## 2.3. Study Rationale

While standard of care NrtIs targeting the HBV, polymerase are able to suppress HBV DNA in most patients, around 30% of HBeAg positive patients and up to 10% of HBeAg negative patients are not able to reach HBV DNA <LLOQ by treatment Week 48. Treatment intensification approaches are needed to increase the proportion of patients able to achieve complete viral suppression (ie, proportion of subjects achieving HBV DNA <LLOQ at Week 48). The HBV core protein is involved in multiple steps in the HBV life cycle, including both viral replication and the establishment of new cccDNA (Belloni 2013; Levrero 2009). Inhibition of HBV core protein represents a novel therapeutic strategy

for the treatment of CHB ([Yang 2019](#)). Analyses of Phase 2a studies, including ongoing open-label study, Study 211, demonstrate that treatment-naïve and virologically suppressed subjects treated with ABI-H0731 + NrtI, compared to those treated with NrtI alone, achieve deeper declines in HBV DNA ([Section 2.2.3](#)).

Based on these data, the addition of ABI-H0731 to NrtI therapy may increase the proportions of subjects with partial virologic suppression able to achieve complete viral suppression, a status that has been shown to correlate with long-term clinical outcomes ([EASL 2017](#), [Paptheodoridis 2015](#), [Yip 2020](#)). The present Phase 2a study (ABI-H0731-205) will explore the safety of ABI-H0731 when added to NrtI and evaluate the antiviral activity of the combination as measured by the proportions of subjects achieving HBV DNA <LLOQ at Week 48. At Week 48 all subjects will receive ABI-H0731+NrtI through Week 96. Following completion of treatment with ABI-H0731 in this study, eligible subjects will undergo follow-up evaluation while continuing standard of care therapy with NrtI until Week 120.

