#### **6.1.2. Blinding**

Study subjects, Investigators and other site personnel administering the study drug, performing the clinical assessments and handling data on the study subjects, will be blinded to individual subject treatments assignments (ie, PBO+NrtI or ABI-H0731+NrtI) throughout the duration of the study. To support maintenance of the study blind, HBV pgRNA results will not be provided to the study subjects, Investigators or other site personnel until completion of the study.

A limited internal Sponsor team will be unblinded to individual subjects' treatment assignments throughout the study to ensure timely analysis of any emergent safety/tolerability issues, and completion of the prespecified safety data reviews. The unblinded individuals will be identified in the Statistical Analysis Plan (SAP) along with their specific roles and responsibilities. All other Sponsor personnel will remain blinded until completion of the study. The contract research organization's (CRO's) Medical Monitor may be unblinded to individual subjects' treatment assignments where required for assessment of emergent safety/tolerability issues.

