#### **6.1.3. Unblinding in Emergency Situations**

Requests can be made to unblind an individual study subject for emergencies or urgent situations. Prior to unblinding, and if the situation permits, the Investigator should first contact the Sponsor and/or authorized Medical Monitor to discuss the case. However, the final decision whether to unblind a subject will be the Investigator's decision, and the Investigator need not wait for the unblinding permission to be granted by the Sponsor/CRO Medical Monitor in emergency situations where identification of the individual treatment assignment is required for the immediate medical management of the subject. Access to the unblinded treatment assignment should be limited to the minimum number of people required for emergent management of the subject. The actual treatment assignment must not be disclosed to the subject and/or other study personnel, including site monitors and office staff; nor should there be any written or verbal disclosure of the code in the subject's study documents.

The request for unblinding should include the protocol number, site number, subject number, treating Investigator's contact info, a detailed reason for the unblinding, and date the information is needed. All

key correspondence between the requestor and Sponsor or CRO Medical Monitor should be saved in the Trial Master File.

The IRT system will be used as the unblinding tool. In the event that an individual subject's treatment assignment is unblinded, the date and reason that the blind was broken must be recorded in the source documentation. Any treatment assignments that are unblinded must be immediately reported to the CRO Medical Monitor and the Sponsor. Code-break IRT access is given to the Investigator/designated person at the site and to the designated Medical Monitor(s) for the study.

Following unblinding, the subject will discontinue ABI-H0731 or matching PBO and continue with the study follow-up assessments.

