## **6.2. Description and Handling of ABI-H0731 and Matching Placebo (Investigational Medicinal Product)**

The investigational medicinal products (IMPs) to be used in this study are ABI-H0731 and matching PBO.

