#### **8.7. Pregnancy**

##### **8.7.1. Female subjects who become pregnant**

Any female subject who becomes pregnant while participating in the study will discontinue the study drug(s) immediately.

The Investigator will collect pregnancy information on any female subject who becomes pregnant while participating in this study, including the 24-week follow-up period. The initial information will be recorded on the Pregnancy Reporting form and submitted to the CRO Pharmacovigilance group within 24 hours of learning of a subject’s pregnancy. Refer to the Study Reference Manual for contact information for reporting a pregnancy.

The subject will be followed to determine the outcome of the pregnancy. The Investigator will collect follow-up information on the subject and the neonate and the information will be forwarded to the Sponsor. Generally, follow-up will not be required for longer than 6 to 8 weeks beyond the estimated delivery date. Any termination of pregnancy will be reported, regardless of fetal status (presence or absence of anomalies) or indication for the procedure.

While pregnancy itself is not considered to be an AE or SAE, any pregnancy complication or elective termination of a pregnancy for medical reasons will be reported as an AE or SAE. A spontaneous

abortion (occurring at <22 weeks gestational age) or still birth (occurring at >22 weeks gestational age) is always considered to be an SAE and will be reported as such.

Any post-study pregnancy related SAE considered reasonably related to the study drug(s) by the Investigator will be reported to the Sponsor. While the Investigator is not obligated to actively seek this information in former study subjects, he or she may learn of an SAE through spontaneous reporting.

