## **9. SERIOUS ADVERSE EVENTS**

### **9.1. Definition of SAE**

An SAE is any event that meets any of the following criteria:

- Death
- Life-threatening
- Inpatient hospitalization or prolongation of existing hospitalization
- Persistent or significant disability/incapacity
- Congenital anomaly/birth defect in the offspring of a subject who received ABI-H0731
- Other: Important medical events that may not result in death, be life-threatening, or require hospitalization, may be considered an SAE when, based upon appropriate medical judgment, they may jeopardize the subject and may require medical or surgical intervention to prevent one of the outcomes listed in this definition. Examples of such events are:
  - Intensive treatment in an emergency room or at home for allergic bronchospasm
  - Blood dyscrasias or convulsions that do not result in inpatient hospitalization
  - Development of drug dependency or drug abuse

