Preterm Birth (report using mother's subject ID)	Live birth at 34 to <37 weeks gestational age	Live birth at 28 to <34 weeks gestational age	Live birth at 24 to <28 weeks gestational age	Live birth at <24 weeks gestational age
Spontaneous Abortion or Miscarriage f (report using mother's subject ID) Report only one	Chemical pregnancy	Uncomplicated spontaneous abortion or miscarriage	Complicated spontaneous abortion or miscarriage	NA

Abbreviations: ID=identification; NA=not applicable.

f Definition: A pregnancy loss occurring at <20 weeks gestational age.

Protocol Amendment 1 ABI-H0731-205

08 September 2020

Psychiatric				
Parameter	Grade 1 Mild	Grade 2 Moderate	Grade 3 Severe	Grade 4 Potentially Life-threatening
Insomnia	Mild difficulty falling asleep, staying asleep, or waking up early causing no or minimal interference with usual social and functional activities	Moderate difficulty falling asleep, staying asleep, or waking up early causing more than minimal interference with usual social and functional activities	Severe difficulty falling asleep, staying asleep, or waking up early causing inability to perform usual social and functional activities requiring intervention or hospitalization	NA
Psychiatric Disorders (includes anxiety, depression, mania, and psychosis) Specify disorder	Symptoms with intervention not indicated OR Behavior causing no or minimal interference with usual social and functional activities	Symptoms with intervention indicated OR Behavior causing greater than minimal interference with usual social and functional activities	Symptoms with hospitalization indicated OR Behavior causing inability to perform usual social and functional activities	Threatens harm to self or others OR Acute psychosis OR Behavior causing inability to perform basic self-care functions
Suicidal Ideation or Attempt Report only one	Preoccupied with thoughts of death AND No wish to kill oneself	Preoccupied with thoughts of death AND Wish to kill oneself with no specific plan or intent	Thoughts of killing oneself with partial or complete plans but no attempt to do so OR Hospitalization indicated	Suicide attempted

Abbreviations: NA=not applicable.

Protocol Amendment 1 ABI-H0731-205

08 September 2020

Respiratory				

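### Section 9.1 ties the birth-defect SAE criterion to receipt of ABI-H0731, which blinded sites cannot know for subjects who stop before Week 48; fetal-loss cut-offs also differ between Section 8.7.1 and Appendix 3

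*Combined protocol and SAP*

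**What the plan says.** **Birth defects.** Protocol Section 9.1 includes as an SAE criterion "Congenital anomaly/birth defect in the offspring of a subject who received ABI-H0731". Section 6.2 states: "The investigational medicinal products (IMPs) to be used in this study are ABI-H0731 and matching PBO". The criterion therefore names one of the two investigational products. Under Section 6.1.2, subjects, Investigators and site staff "will be blinded to individual subject treatments assignments (ie, PBO+NrtI or ABI-H0731+NrtI) throughout the duration of the study". Section 9.2 gives 24 hours from awareness to report an SAE. Section 2.3 describes the switch: "At Week 48 all subjects will receive ABI-H0731+NrtI through Week 96". SAP Section 7.1.4 takes the SAE definition from the protocol unchanged.

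**Pregnancy follow-up.** Section 8.7.1 states: "Any female subject who becomes pregnant while participating in the study will discontinue the study drug(s) immediately". It requires pregnancy information on every female subject who becomes pregnant, whatever her arm, with follow-up of the outcome and the neonate. Section 8.7.2 does the same for consenting partners of male subjects who took study drug.

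**Fetal loss.** Section 8.7.1 says that a spontaneous "abortion (occurring at <22 weeks gestational age) or still birth (occurring at >22 weeks gestational age) is always considered to be an SAE". Appendix 3, which Section 8.2 makes the grading scale, places stillbirth at 20 weeks or later (Grade 3 only). Its footnote to spontaneous abortion or miscarriage reads: "Definition: A pregnancy loss occurring at <20 weeks gestational age".

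**The concern.** An Investigator has to be able to apply an SAE definition at the bedside, blinded, within the reporting clock. A criterion that turns on which product the parent took cannot be applied that way while the assignment is concealed. Read literally, it also gives the same event different regulatory handling in the two arms: an SAE with a 24-hour report after ABI-H0731, and not an SAE on this criterion after placebo alone. Appendix 4 says that embryofetal studies in animals have not been done, so the few human outcomes that might arise should be classified consistently.

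The fetal-loss point is a plain inconsistency. A site has to use Section 8.7.1 to name the event and decide that it is serious, and Appendix 3 to grade it, and the two draw the line in different places.

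**Working it through.** No figure in the plan bears on this and no arithmetic applies. The check sets the passages side by side.

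**Step 1. To whom does the Section 9.1 criterion apply, and can the site tell?**

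| Subject | Has received ABI-H0731? | Can the blinded site tell? | Criterion met? |
|---|---|---|---|
| Group 1, treatment ends before Week 48 | Yes | No | Yes |
| Group 2, treatment ends before Week 48 | No | No | No |
| Either group, treated past the Week 48 switch | Yes | Yes, by design | Yes |

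The difficulty is confined to the first two rows. Those rows include every female subject who becomes pregnant before Week 48, because she stops study drug at once and does not reach the phase in which exposure is known. For a male subject who continues past Week 48 the criterion is met whichever group he was in. That holds even if his partner conceived while he was on placebo, since the wording does not link exposure to the time of conception.

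**Step 2. Does another route capture the event?**

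- Section 8.7.1 collects the outcome and neonatal information in both arms. The pregnancy itself has a 24-hour reporting form, but no time limit is stated for forwarding the neonatal follow-up. Only spontaneous abortion and still birth are declared always to be SAEs there; an anomaly in a live-born infant is not named.
- The important-medical-event criterion in Section 9.1 is discretionary and is framed around jeopardy to the subject. It could be used, but does not clearly reach an anomaly in the offspring.

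Outcome capture is therefore neutral between arms. The explicit birth-defect SAE classification, and with it the SAE reporting clock, is not.

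**Step 3. Is the restriction deliberate?** Neighbouring text suggests not. Section 8.7.2 speaks of male subjects who receive the study drug, without naming a product, and SAP Section 7.1.3 describes an AE form that asks about relationship to ABI-H0731 or placebo together.

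**Step 4. Compare the fetal-loss cut-offs.**

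| Gestational age at loss | Section 8.7.1 | Appendix 3 |
|---|---|---|
| Below 20 weeks | Spontaneous abortion, always an SAE | Spontaneous abortion, Grade 1 to 3 |
| 20 to below 22 weeks | Spontaneous abortion, always an SAE | Stillbirth, Grade 3 |
| Exactly 22 weeks | Neither class | Stillbirth, Grade 3 |
| Above 22 weeks | Still birth, always an SAE | Stillbirth, Grade 3 |

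From 20 to below 22 weeks the term differs, and so can the grade: an uncomplicated loss graded as a spontaneous abortion would be Grade 2, and graded as a stillbirth Grade 3. Seriousness is the same under either term. Only at exactly 22 weeks does the automatic SAE rule fail to apply as written.

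**The case against.** The strongest reply is that little turns on either point. Pregnancy outcomes are reported whatever the arm. A blinded site that cannot exclude ABI-H0731 can simply report. Section 6.1.2 provides a limited unblinded Sponsor team and allows the CRO Medical Monitor to be unblinded for safety assessment, so exposure can be checked without opening the site blind. At exactly 22 weeks, Section 8.7.1 still requires a pregnancy complication to be reported as an AE or SAE. All of this stands and it limits the point. It does not make the Section 9.1 wording right: a rule that works only if sites disregard its restriction should not contain the restriction.

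A reader might infer more than the documents support:

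- *Sites would have to unblind, and unblinding would force discontinuation.* Section 6.1.3 offers this route for limited circumstances: "Requests can be made to unblind an individual study subject for emergencies or urgent situations". Classifying an event is not an obvious fit. A pregnant woman has already stopped study drug, so the discontinuation rule adds nothing for her. It could matter only for a male subject with a pregnant partner, and the unblinded Sponsor team or Medical Monitor could resolve exposure instead.
- *The placebo-period count would be zero by definition.* Sites that do not know the arm cannot filter out placebo cases, a Group 2 man who continues past Week 48 meets the criterion, and the other SAE criteria do not depend on arm. The literal exclusion covers only subjects never exposed to ABI-H0731.
- *A randomised safety comparison would be biased.* SAP Section 3 plans no statistical analysis, and SAP Section 7.1.6 lists all AEs for all randomized subjects. No between-arm comparison remains to be biased.
- *Some number of such events should be expected.* The documents give no pregnancy or birth-defect rate, so no expected count can be stated.

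**Conclusion.** The point holds as two wording defects. First, the birth-defect criterion in Section 9.1 cannot be applied blind for subjects whose treatment ends before the Week 48 switch, and it literally omits those who took only placebo. The consequence is limited to SAE classification and 24-hour SAE reporting. Second, Section 8.7.1 and Appendix 3 disagree for losses from 20 to below 22 weeks, which affects term and grade, and Section 8.7.1 leaves exactly 22 weeks unassigned.

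The SAP introduction reports 2 subjects randomized at early termination, so the effect on this study is probably negligible. The correction is worth making because it concerns a stated safety-reporting rule, and it matters most if the text is carried into another protocol. The conclusion assumes that Section 9.1 is applied as worded and that no supporting manual overrides it; the study manuals cited in the protocol are not among the documents.

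**What to change.** In Section 9.1, replace the reference to receipt of ABI-H0731 with receipt of study drug (ABI-H0731 or PBO). No separate mention of partners' pregnancies is needed, because offspring of a subject already covers male subjects. SAP Section 7.1.4 then inherits the corrected definition without change.

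Reconcile Section 8.7.1 and Appendix 3 to a single gestational cut-off, worded so that every gestational age falls in exactly one class. The sponsor should decide which cut-off to use.

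The cost is two text edits. The only downside is that a birth defect after placebo alone would also be classified and reported as an SAE, which is what a blinded site would have to do in practice anyway. If this protocol is not amended again, the edits belong in any later protocol that reuses these sections.

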#### **Definition of Terms**

**Life-threatening:** An AE is life-threatening if the subject was at immediate risk of death from the event as it occurred; ie, it does not include a reaction that if it had occurred in a more serious form might have caused death. For example, drug induced hepatitis that resolved without evidence of hepatic failure would not be considered life-threatening even though drug induced hepatitis can be fatal.

**Hospitalization:** AEs requiring hospitalization should be considered SAEs. Hospitalization for elective surgery or routine clinical procedures that are not the result of AEs (eg, elective surgery for a pre-existing condition that has not worsened) need not be considered AEs or SAEs. If anything untoward is reported during the procedure, that occurrence must be reported as an AE, either “serious” or “non-serious” according to the usual criteria.

In general, hospitalization signifies that the subject has been detained (usually involving at least an overnight stay) at the hospital or emergency ward for observation and/or treatment that would not have been appropriate in the physician's office or outpatient setting. When in doubt as to whether “hospitalization” occurred or was necessary, the AE should be considered serious.

**Disability/incapacitating:** An AE is incapacitating or disabling if the experience results in a substantial and/or permanent disruption of the subject's ability to carry out normal life functions.

### **9.2. Reporting Serious Adverse Events**

All SAEs must be reported within 24 hours of learning about the event using the SAE Report form to the CRO Pharmacovigilance group. Refer to the Study Reference Manual for contact information for reporting SAEs.

The initial report should be promptly followed by detailed, written reports, which will include copies of relevant hospital case reports, autopsy reports, and other documents when requested and applicable. This additional information will be requested, if necessary, by the responsible monitor within 5 days of receipt of the alert report. This is to ensure that the initial reporting of SAEs is made to regulatory authorities within the required time period.

For a follow-up report to the authorities, the monitor may be required to collect further information for a final evaluation of the case. Reporting to the respective country regulatory authorities will be the responsibility of the Sponsor and the CRO.

The CRO will be responsible for informing all central Institutional Review Boards (IRBs)/ Independent Ethics Committees (IECs) of SAEs as required. It will be the responsibility of the individual Investigators to inform any local IRBs/IECs of SAEs as required. Correspondence with the IRB(s)/IEC(s) relating to the reporting of SAEs will be retained in the study file.

### **9.3. Overdose**

An overdose is defined as the accidental or intentional administration of any dose of a product that is considered both excessive and medically important. The Medical Monitor may be contacted for questions concerning potential cases of overdose. An overdose is not in and of itself considered to be an AE unless it results in untoward medical effects. Any AE associated with an overdose or incorrect administration of study drug should be entered in the subject's source documentation and Adverse Event eCRF. If the associated AE fulfills the criteria of an SAE, then the event should be reported to the Sponsor or CRO within 24 hours after the site learns of the event.

### **9.4. Management of On-treatment and Post-treatment ALT Elevations**

All subjects participating in the study will be closely monitored for ALT elevations and/or signs of potential decline in hepatic function. Subjects experiencing ALT elevations  $\geq 2 \times$  Baseline or on-treatment nadir and  $> 2 \times$  ULN during study treatment or during post-treatment follow-up should be closely monitored with regular unscheduled visits every 1 to 2 weeks at the discretion of the Investigator. For these subjects, at each timepoint, an Unscheduled Visit should be conducted with completion of assessments as described in [Section 7.7](#). Additionally, the following guidance is provided for management of subjects with ALT elevations:

- All subjects with an ALT elevation on treatment, defined as ALT  $> 2 \times$  Baseline or on-treatment nadir and  $\geq 10 \times$  ULN, should have the ALT findings confirmed within 3 days of receipt of the original results. To confirm the ALT finding, the subject should return to the clinic for an Unscheduled Visit and undergo all assessments as noted in [Section 7.7](#) (Unscheduled Visit).
- If the ALT elevation is confirmed, then an additional Unscheduled Visit will be performed to further evaluate the subject. At this visit, the following laboratory tests will be performed: ALT, AST, total bilirubin (if total bilirubin is elevated, reflex to Direct Bilirubin), serum albumin, HBV DNA, and quantitative HBV serologies (HBeAg [reflex qualitative HBeAg if quantitative HBeAg is negative] and HBsAg [reflex qualitative HBsAg if quantitative HBsAg is negative]), HAV IgM, HCV RNA, HDV RNA, and HEV IgM.
  - If an intercurrent illness is determined to be causal, subjects with an ALT elevation without declining hepatic function and without contraindications may continue

treatment and the intercurrent illness should be treated as deemed medically appropriate by the Investigator.

- Subjects with an ALT elevation without declining hepatic function and without contraindications may continue treatment with study drug under close observation.
- If ALT is rising at the confirmatory visit, subjects should return for an **Unscheduled Visit** every 2 to 5 days until the ALT elevation has stabilized. At these visits the following laboratory tests will be performed: ALT, AST, total bilirubin (if total bilirubin is elevated, reflex to Direct Bilirubin), serum albumin, INR, HBV DNA, and quantitative HBV serologies (HBeAg [reflex qualitative HBeAg if quantitative HBeAg is negative] and HBsAg [reflex qualitative HBsAg if quantitative HBsAg is negative]). Subjects whose ALT has stabilized should continue to be monitored weekly (or more frequently, as deemed necessary by the treating physician) until ALT values return to normal or Baseline levels.
  - Subjects with an ALT elevation without declining hepatic function and without contraindications should discontinue study drug if the ALT remains persistently elevated for >4 weeks
- Subjects with confirmed ALT elevation with evidence of declining hepatic function should be discontinued from study treatment. This is defined as:
  - ALT elevation  $\geq 2 \times$  Baseline or nadir and  $> 2 \times$  ULN AND
    - Direct bilirubin increase to  $\geq 2 \times$  Baseline and  $\geq 2 \times$  ULN OR
    - Albumin decline  $\geq 0.5$  g/dL OR INR  $> 2 \times$  Baseline OR
    - Symptoms of liver inflammation (eg, fatigue, weakness, lack of appetite, nausea, vomiting, jaundice, or discolored feces)
- Subjects with evidence of declining hepatic function should return for an **Unscheduled Visit** every 2 to 5 days until the relevant laboratory values stabilize. Subjects whose hepatic function has stabilized should continue to be monitored weekly (or more frequently as deemed necessary by the Investigator) until the relevant laboratory values return to normal or Baseline.
- **Post-treatment ALT Elevation**

Following cessation of study drug treatment under this protocol all subjects will be closely followed for ALT elevations and/or signs of potential decline in hepatic function. This applies to all subjects whether they prematurely discontinue study drug or complete the study per protocol. Any subject with a post-treatment ALT elevation without evidence of declining hepatic function or a post-treatment ALT elevation with evidence of declining hepatic function as defined above, will be evaluated as noted above.

All subjects with ALT elevation without or with declining hepatic function (on or off-treatment) should continue to be followed on their regular study visit schedule, with the addition of unscheduled visits as described above. If the post-treatment ALT elevation has not substantially resolved by the last study follow-up visit, subjects should continue to return to clinic as deemed medically appropriate by the Principal Investigator, in consultation with the Sponsor, and the unscheduled visit module in the case report form should be utilized as needed to gather additional clinical and laboratory data until the ALT

Protocol Amendment 1 ABI-H0731-205  
08 September 2020

---

elevation is documented to be either resolved or resolving (defined as consistent ALT declines of 10% or more or normalization of ALT) on at least 2 successive visits.

If 5 or more subjects meet these ALT elevation management criteria, the US FDA and other relevant regulatory agencies will be notified, and subsequent steps will be determined after consultation with these agencies.

